### 6.4 SAMPLE SIZE DETERMINATION

Sample size estimates were calculated based on unpublished data indicating an incidence of concussion of 11%, and published data on the reduction in concussion risk associated with increased neck strength. Based on this information, a sample of size of 1198 subjects would be needed to detect a correlation of R=0.25 between neck strength and a reduction in the severity of concussion symptoms (based on cognitive assessment scores) with a power of 0.8 at alpha=0.05. Assuming attrition of 15-20%, we therefore believe that approximately 1500 subjects will be needed.

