# 4 STUDY PROTOCOL

### 4.1 **OVERVIEW**

This project has the following goals:

- 1. Determine whether baseline measurements of neck strength correlate with the incidence, severity, and duration of concussion symptoms;
- 2. Determine whether a standardized neck strengthening training regime reduces the risk of concussion and the severity and duration of symptoms; and
- 3. Determine whether the relationships between neck strength and the clinical symptoms of concussion are independent of gender.

Subjects aged 5 to 22 who are involved in organized, academic or community-based contact/collision sports activities at Gustavus Adolphus College, member schools of the Independent Metro Athletic Conference (IMAC) conference, and The Sanneh Foundation participate in an instructor-led neck-strength training program. Subjects enrolled in the study will be followed for up to 3 years to assess whether the incidence, severity, and duration of concussion symptoms varies as a function of neck strength in young athletes. Anthropometric measurements, neck strength parameters, cognitive assessments, and an eye-tracking assessment will be performed for each subject at baseline, and at yearly intervals thereafter in the absence of a reported head injury. In addition, anthropometric and neck-strength measurements will be recorded at regular intervals during the study to quantify the effectiveness of the strength training regime. Subjects diagnosed with concussion during the study will be assessed for the severity and duration of postconcussion symptoms using eyetracking methodology and traditional cognitive assessments. Clinical outcomes will be assessed immediately following a concussive event and monitored by research staff until symptoms resolve. Data will be collected by onsite study volunteers trained by [name] or another member of the Brain Injury Research Lab staff at HCMC. All aspects of the study design will be overseen and approved by [name].

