#### Assessments and timeline

Demographic and sport history information will be collected at screening, and morphometric, cognitive, neck-strength, and eyetracking assessments will be made at baseline, and annually thereafter in the absence of a reported head injury. In addition, anthropometric and neck-strength measurements will be recorded immediately before and after training sessions at 6-month intervals to track improvements in neck strength. Subjects who experience concussion during the study will undergo assessments for eye-tracking and cognition at the time of the event; a subset of cognitive assessments will also be made on a daily basis following the event, until full recovery is achieved. If recovery is not achieved within a week, eye-tracking will be repeated. If symptoms continue to persist, additional cognitive assessments will be administered and repeated monthly until the subject fully recovers.

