### 6.3 STATISTICAL METHODS

Data accrued through this study will be reviewed with statisticians from The Minnesota Medical Research Foundation Chronic Disease Research Group. Repeatedmeasures analysis of variance (ANOVA) will be used to evaluate the effectiveness of the training program for increased neck strength. Relationships among neck-strength parameters and concussion risk and functional outcome measures will be evaluated via logistic and linear regression models. Analyses will be adjusted for sex to evaluate whether the results are independent of gender.

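### Neck strength is related to post-concussion cognitive scores with sex as the only named covariate, so prior ability and age may enter the severity result

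*Protocol*

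**What the plan says.** Severity is part of the primary hypothesis (protocol 4.4), and it is the outcome on which the study is sized. Section 6.4 asks for power to detect R = 0.25 for the relation of neck strength to "a reduction in the severity of concussion symptoms (based on cognitive assessment scores". Section 6.3 names logistic and linear regression for risk and functional outcome, and one adjustment: "Analyses will be adjusted for sex to evaluate whether the results are independent of gender". Neither age nor the pre-injury score is named. Section 6.4.1, on complicating considerations, discusses only the balance of males and females.

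The design is observational with a single arm (4.2, Table 1), and enrolment runs from age 5 to age 22 (4.5.1). Every subject has a cognitive and an eye-tracking assessment at baseline (4.8.1). Table 1 adds that the "assessments will be made at baseline, and annually thereafter in the absence of a reported head injury", and section 4.1 likewise places the repeats "at yearly intervals thereafter in the absence of a reported head injury". Cognitive scores are taken again after a concussion (4.8.3 to 4.8.5). No section says whether severity is the raw post-injury score, a change from the subject's own earlier score, or an age-normed score.

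**The concern.** A post-injury cognitive score combines the level the subject had before the injury with the deficit the injury caused. Only the deficit is severity. In a group aged 5 to 22, both neck strength and raw cognitive performance can be expected to rise with age, and no randomisation separates the two. A regression of the raw score on neck strength, adjusted for sex alone, could then show that stronger necks go with milder concussions when the injury deficit has no relation to strength.

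Even without that bias, differences in prior ability add variance unrelated to the injury and make a true relation harder to see. The data that would remove much of both problems are already collected on every subject, but the stated model does not use them.

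**Working it through.** **Inputs from the protocol (6.4).** R = 0.25; "with a power of 0.8 at alpha=0.05" (taken here as two-sided); "unpublished data indicating an incidence of concussion of 11" per cent; "a sample of size of 1198 subjects would be needed"; attrition 15-20%; about 1500 enrolled.

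**Inputs assumed, not in the protocol.** The correlation rho between pre- and post-injury scores, and the correlations of age with neck strength (a) and with raw score (b).

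**The plan's own figure.** By Fisher's z, the number of concussed subjects needed is ((1.96 + 0.8416)/atanh(0.25))² + 3 = (2.8016/0.2554)² + 3 = 123.3, so 124. Dividing by 0.11 gives 1128 subjects, not 1198. The stated 1198 yields 1198 × 0.11 = 131.78, about 132 concussed, with power Φ(0.2554 × √128.78 − 1.96) = 0.83. The attrition step reproduces: 1198/0.80 = 1498, about 1500. The gap between 1128 and 1198 is a separate matter; 132 concussed is used below.

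**Case A: age links strength and score, and there is no severity effect.** The spurious correlation is R = a × b. The chance of a significant result is Φ(atanh(R) × √128.78 − 1.96), plus a negligible opposite tail.

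| a, b (either order) | Spurious R | Chance of a significant result |
|---|---|---|
| 0.3, 0.3 | 0.09 | 18% |
| 0.3, 0.5 | 0.15 | 40% |
| 0.3, 0.7 | 0.21 | 68% |
| 0.5, 0.5 | 0.25 | 83% |
| 0.5, 0.7 | 0.35 | 99% |
| 0.7, 0.7 | 0.49 | about 100% |

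With both at 0.5, the artefact equals the planned effect.

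**Case B: the pre-injury score is unrelated to strength.** If R = 0.25 holds for the baseline-adjusted score, the raw score gives R = 0.25 × √(1 − rho²).

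| rho | Variance share of baseline (rho²) | Raw R | Power at 132 |
|---|---|---|---|
| adjusted | – | 0.250 | 0.83 |
| 0.5 | 25% | 0.217 | 0.70 |
| 0.6 | 36% | 0.200 | 0.63 |
| 0.7 | 49% | 0.179 | 0.54 |
| 0.8 | 64% | 0.150 | 0.40 |

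Over a wider range, rho = 0.3 gives a 9% share and power 0.79; rho = 0.9 gives 81% and 0.24.

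**The cases are alternatives and must not be added.** Case B needs baseline and strength to be unrelated; Case A has age linking strength and score. If baseline correlates 0.2 with strength, the raw R is 0.2 × rho + 0.25 × √(1 − rho²): 0.10 + 0.217 = 0.32 at rho = 0.5, and 0.16 + 0.15 = 0.31 at rho = 0.8. R then rises above 0.25, so the harm is bias and not lost power.

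**Sensitivity to the event count.** Section 6.4 does not say over what period the 11% applies. If it is per year over a full 3 years, a Poisson mean of 0.33 gives 1198 × (1 − e^−0.33) = 337 concussed. Case B power is then 0.98, 0.96, 0.91 and 0.79 for rho 0.5 to 0.8, so that loss shrinks. Case A gets worse: for the smallest spurious R, Φ(0.0902 × √334 − 1.96) = 38% in place of 18%.

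**Recurrence (Poisson, all 1500 followed throughout).** With mean 0.11 over the whole study, 1500 × (1 − e^−0.11) = 156 are concussed and 1500 × (1 − 1.11 × e^−0.11) = 8 more than once. With mean 0.33, the figures are 422 and 66. The second pair belongs to the per-year reading and cannot be combined with 132 events.

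**The case against.** The strongest reply is that the protocol is silent and not wrong. A reader might infer from 6.4 that severity is the raw score, read without regard to the subject's own baseline. The text does not say so. Its wording fits a raw, change, baseline-adjusted or age-normed score equally well, and collecting a baseline on everyone suggests that some comparison is intended. Section 6.3 says that analyses will be adjusted for sex, not for sex alone. Score derivation and the full covariate list often stand in an analysis plan, which is not at hand. All of this stands, and it limits the point to what may happen if 6.3 is followed as written. It does not remove the point: 6.3 goes as far as naming the models and one covariate, and adding baseline score and age improves that stated model.

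A reader might also infer that severity would mostly measure ability and maturity. The protocol does not support this. It gives no pre/post correlation and does not name the cognitive instruments (4.7, 6.2), so age-norming cannot be ruled out, and the baseline share runs from 9% to 81% over the assumed range.

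Third, a reader might infer that the condition on yearly assessments leaves injured subjects without a usable reference. For a first concussion it does not: the yearly schedule runs up to the injury, so a score about a year old or newer should exist. For a later concussion, Table 1 follows cognition daily and then monthly to recovery, which leaves scores near recovery, although the daily ones are only a subset of the battery. The condition may also merely separate the routine schedule from the post-concussion one.

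**Conclusion.** The point holds in a limited form. The protocol relates neck strength to a cognitive severity measure across ages 5 to 22, names sex as the only covariate, and nowhere links severity to the pre-injury score it collects. The resulting association may therefore reflect prior ability and maturity.

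Confounding by age is the more serious risk, because more events make it worse. Its size depends entirely on assumed correlations: a spurious R of 0.09 to 0.49 and an 18% to near 100% chance of a false positive at about 132 concussed. The loss of power from 0.83 to 0.70-0.40 is a separate scenario, valid only if baseline is unrelated to strength, rho is 0.5 to 0.8 and the raw score is used. If scores are age-normed, or the analysis plan already adjusts for baseline and age, much or all of the problem disappears. The reference score for recurrent concussions is a minor matter.

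**What to change.** In 6.3 and 6.4, state that post-injury cognitive and eye-tracking scores are analysed by regression on neck strength with the subject's latest pre-injury score of the same measure and age as covariates, alongside sex. Age is needed as well as the baseline score, because it is the confounder at issue and a baseline up to a year old need not capture all of it in growing children. Say in 6.4 that R = 0.25 refers to this adjusted relation. The cost is wording: age and the baseline scores are already collected, and the model gains two terms.

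As a secondary change, base the main severity and duration analysis on each subject's first on-study concussion. This keeps every concussed subject and drops only repeat events: those of about 8 of 156 concussed subjects if the 11% covers the whole study, and of at most about 66 of 422 if it is per year with everyone followed for 3 years.

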# 6.4.1 Data Analysis and Complicating Considerations

A potential limitation on data interpretation is that substantial asymmetry in the number of enrolled males vs females could reduce the potential to detect an effect of neck strength on concussion risk. This is more likely to occur if the enrolled population is heavily skewed towards males because of the lower incidence rate of concussion in this demographic. All efforts will be made to enroll a study population with a 50% male-to-female ratio. We will consult with a biostatistician if this target is not reached to reevaluate the adjusted minimum sample size required to detect an effect.

# 7 INVESTIGATOR RESPONSIBILITIES AND OBLIGATIONS

### 7.1 INVESTIGATOR RESPONSIBILITIES

### 7.1.1 Investigator Accountability

The Investigator is ultimately responsible for equipment accountability including but not limited to hand-held tension devices and eye trackers. The study-site coordinators, or designees, are responsible for maintaining site logs of equipment accountability and use, which will include tracking the receipt and return/disposition of all equipment used in the study (if applicable).

# 7.1.2 Patient Accountability

A subject /subject caregiver may withdraw their consent to participate in the study at any time and can do so by notifying the Investigator and/or Investigator staff.

### 7.2 INVESTIGATOR REPORTS

The Investigator will be responsible for the following reports:

### **Adverse Events:**

Adverse events will be reported to the reviewing IRB in compliance with its reporting requirements. For serious adverse events (whether or not related to the intervention) or unanticipated adverse effects of the intervention, this will occur no later than 5 business days of the Investigator becoming aware of the event.

# **Deviations from the Investigational Plan:**

The Investigator is responsible for reporting all protocol deviations. Examples of protocol deviations include, but are not limited to:

- Failure to obtain written informed consent prior to conducting study procedures
- Failure to comply with any requirements of the reviewing IRB

**Progress Reports:** The Investigator is required to submit annual progress reports to the reviewing IRB. Reports must include the number of study subjects, a summary of all follow up evaluations, a summary of all adverse events and a general description of the study's progress.

**Final Report:** The Investigator will submit a final report to the IRB within 3 months of termination of the study or termination of that Investigator's participation in the study.

#### HSR# 17-4360

# 7.3 INVESTIGATOR RECORDS

The Investigator will maintain complete, accurate and current study records, including the following materials:

- Study subject records, including signed informed consent forms and copies of all data collection forms
- Documentation of any participation in the study without informed consent and a brief description of the circumstances justifying the failure to obtain informed consent
- All relevant observations, including records concerning adverse effects of the training regime (whether anticipated or unanticipated)
- Current study protocol and documentation of protocol deviations, including details of any reason for deviations from the protocol that could affect the scientific quality of the study or the rights, safety, or welfare of the subjects,
- The IRB-approved blank informed consent form and blank data collection forms
- Certification that the investigational plan has been approved by all of the necessary approving authorities
- Signed and dated letters of agreement among the Investigator and all participating study site organizations.

These records shall be maintained for a period of 2 years after the date on which the investigation is terminated or completed.

# 7.4 MONITORING

After commencement of the study, regular monitoring will be conducted to ensure:

- Ongoing compliance with the study protocol
- Ongoing compliance with any conditions of approval of the reviewing IRB

# 7.5 SCREENED SUBJECTS NOT ENROLLED

Only data for enrolled subjects will be monitored and entered into the database. Of those subjects who have consent and are screened for the study but are not enrolled for any reason will not be followed and their data will not evaluated, except as may be necessary to assess the reason for the screening failure. The sites may retain the informed consent form and screening documentation for these subjects at their discretion.

HSR# 17-4360

# 8 **REIMBURSEMENTS**

### 8.1 SUBJECT COMPENSATION

There will be no costs to the subject or payment for participation in the study to subjects or their legal proxies.

